Proprioceptive neuromuscular facilitation (PNF) are synergistic pattern of movement with the emphasis of facilitating normal movement, the proposed mechanism for some types of PNF that they are reliant on the facilitation of golgi tendon organs and muscle spindles which are responsible for two reflexes 1. autogenic inhibition 2. Reciprocal inhibition, although there is conflicting evidence regarding the mechanisms of PNF the beneficial effects are well established on many conditions like range of motion, neuromuscular functions, lymphedema and many more.

Most of the studies that tested PNF on the cervical region measured range of motion, flexibility and strength. Studies conducted to influence cervical proprioception used multiple interventions such as head relocation practice, eye/head coordination exercises, muscle vibration, mental training, strength and motor control exercises.

Due to the importance of cervical proprioception and the lack of studies in literature, the Purpose of this study is to investigate the acute influence of proprioceptive neuromuscular facilitation on cervical proprioception, range of motion and strength.

Study Design: This is a double-blinded randomized controlled trial. Participants were not aware of their assigned group, also the assessor was blinded to group allocation.

Sample Size: The sample size was calculated by using G*Power 3.1.7 for Windows (G*Power©, University of Dusseldorf, Germany), by using f family test ANOVA repeated measures and between factors, with statistical power of 0.80 (1-B error Probability) and alpha error level probability of 0.05 and effect size of 0.25 with number of measurements being 2, which total to 120 participants.

Participants will be recruited from university campus by directly asking students from classes if they can volunteer by explaining that the trial will involve the cervical region, also mentioned that is one-time session that can take up to an hour. Participants then will be handed consent forms that included more details about the trial.

Inclusion Criteria:

- Neck disability index score of 5 or less
- Able to understand and follow instructions
- Above 18 years old

Exclusion Criteria:

- Cervical trauma
- History of cervical inter-vertebral disc pathology
- Rheumatic diseases
- Whiplash syndrome
- History of surgeries to the neck, face and shoulders
- History of systemic diseases

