Randomization and Procedures Randomization done by a person external to the study. Participants that signed the consent form and meet the inclusion criteria were assigned a number which corresponded to one of the three groups. Participants were asked to enter a room where the assessor performed the first measurements, then participants were asked to go to a separate room where the treatment methods took place. The therapist corresponded the number of the participant to the randomization sheet and applied the assigned treatment. After that participants were asked to go back to the first room for the second measurement. Participants were asked not to make a comment to the assessor but they can direct any question to the therapist.

ASSESSMENT METHODS

Cervical Proprioception: The cervical proprioception will be done using cervical range of motion instrument (CROM, Performance Attainment Associates, Lindstrom, MN, USA) using the joint position accuracy method of proprioception assessment, the device is made of a plastic frame that rest over the head, nose and ears, with a strap to secure it, it has three inclinometers attached to the frame, one in the sagittal plane, the second in the frontal plane and the third in the horizontal plane, which makes able to measure all 6 directions of movement. This instrument was reliable and valid to assess cervical proprioception, the chosen target angle is 30 degrees.

Cervical proprioception was done for flexion, extension, right side bending, left side bending, right and left rotation.

Participants will be asked to sit and put on the CROM instrument, then they will be instructed to start moving their head to one of directions then the assessor will stop them at 30 degrees and tell them to feel the amount of movement and muscle tension, this will be repeated 3 times as a reference, then they will be asked to do the movement with the eyes closed until they reach the target angle, this will be repeated for 3 times, this will be done for each direction and the assessor will record the results.

Range of Motion and Muscle Strength Measurement:

Active Range of motion (AROM) will be measured using CROM instrument, the validity and reliability of CROM to assess ROM is well documented in the literature, AROM was taken for all movement directions.

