Statistical analyses will be performed using SPSS software version 25. Descriptive analyses will be presented using means and standard deviations for continuous data and frequencies and percentages for categorical data. The variables investigated using Kolmogorov Smirnov test to determine whether or not they are normally distributed. Since the variables are normally distributed, ANOVA will be used to compare the means of the groups., Levene test will be used to assess homogeneity of variances. When an overall significance will be observed, pairwise post-hoc tests will be performed using Tukey's test. Since the variables are not normally distributed Kruskal-Wallis test will be used to compare the groups. The Mann-Whitney U test will be performed to test the significance of pairwise differences using Bonferroni correction to adjust for multiple comparisons. Since the variables are normally distributed, the effect of time change in measurements will be investigated by Repeated Measures ANOVA test. Greenhouse-Geisser correction will be used when sphericity assumption is violated. Since the variables are not normally distributed Friedman test will be used. The Wilcoxon test will be performed to test the significance of pairwise differences using Bonferroni correction to adjust for multiple comparisons. A 5% type-I error level was used to infer a statistical significance.

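### With only two measurements, the Friedman test for non-normal variables is the sign test; the plan then has two tests for one pre-post contrast and does not say which decides

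*Combined protocol and SAP*

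**What the plan says.** The Sample Size paragraph plans for "effect size of 0.25 with number of measurements being 2". The Randomization and Procedures section matches this: "the assessor performed the first measurements" before treatment, and "After that participants were asked to go back to the first room for the second measurement". No later assessment is described.

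The Statistical Analysis Plan, repeated in the Statistical Methodology row of the study summary, gives two routes for the effect of time. Normal variables go to repeated-measures ANOVA, with Greenhouse-Geisser when sphericity fails. For the others, "Since the variables are not normally distributed Friedman test will be used", and then "The Wilcoxon test will be performed to test the significance of pairwise differences using Bonferroni correction to adjust for multiple comparisons". On the significance level it says "A 5% type-I error level was used to infer a statistical significance".

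The plan does not state:

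- whether a significant Friedman result is needed before Wilcoxon is read;
- which of the two results is the conclusion;
- whether the time test is run within each arm or on all participants together;
- whether tests are one- or two-sided.

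**The concern.** An overall test, pairwise follow-up, Bonferroni and a sphericity correction together make a template for three or more time points. This trial has two. There is one pair of times, so the follow-up repeats the overall question with a different test, and the first test uses only the direction of each participant's change.

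Three outcomes (joint position accuracy, active range of motion, strength) in six directions give 3 × 6 = 18 variables, and any judged non-normal takes this route. For each one, the pre-post conclusion could depend on a choice between two tests made after the data are seen. If Friedman is the test that counts, a moderate acute change may be missed more often than necessary.

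**Working it through.** **Inputs.** From the documents: two measurements, 120 participants, three arms, 5% level. Assumed: 40 per arm (the allocation ratio is not given), two-sided tests, and every effect size and distribution shape below.

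**1. The plan's own figure.** The sample size is for the between-group factor of a repeated-measures ANOVA, "with statistical power of 0.80 (1-B error Probability) and alpha error level probability of 0.05 and effect size of 0.25". The noncentrality is λ = f²·N·m / (1 + (m − 1)ρ). The plan gives no correlation; with ρ = 0.5 assumed, λ = 0.0625 × 120 × 2 / 1.5 = 10.0 on (2, 117) degrees of freedom, and power is 80.5%. So 120 is reproduced. It does not rest on any within-person time test.

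**2. Friedman with two times.** Let n₊ participants go up and n₋ go down, with no ties, so n = n₊ + n₋. The rank sums are n + n₊ and n + n₋. Then

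χ² = [12 / (n·2·3)]·[(n + n₊)² + (n + n₋)²] − 3n·3 = (n₊ − n₋)² / n.

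This is the uncorrected sign-test statistic. With tie correction the identity also held in 200 generated data sets (largest difference 5e-14). The size of the change does not enter.

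**3. True size at n = 40.** The 5% critical value is 3.84. A 26–14 split gives 12²/40 = 3.60 (not significant); 27–13 gives 14²/40 = 4.90 (significant). Rejection needs 27 or more in one direction, which has two-sided probability 3.85% under the null. Requiring both Friedman and Wilcoxon to be significant brought the rejection rate to about 2 to 3% in simulation.

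**4. Power at n = 40, simulated, two-sided 5%.** Normal and Laplace effects are in SDs of the change; skewed-score effects are reductions in the score.

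| Assumed data | Friedman | Wilcoxon | Wilcoxon gated by Friedman |
|---|---|---|---|
| Normal changes, 0.40 SD | 48% | 68% | 47% |
| Normal changes, 0.47 SD | 61% | 81% | 60% |
| Absolute error, mean of 3 trials, 25% lower | 56% | 75% | 54% |
| Absolute error, mean of 3 trials, 20% lower | 36% | 54% | 34% |
| Gamma scores with shared person component, 20% lower | 61% | 78% | 59% |
| Lognormal scores, 30% lower | 66% | 82% | 65% |
| Laplace changes, 0.40 SD | 79% | 82% | 74% |

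For normal changes the Friedman figure can be checked by hand. At 0.47 SD the chance of a positive change is Φ(0.47) = 0.681, and the binomial chance of at least 27 of 40 is 61%.

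At about 80% Wilcoxon power the Friedman loss depends strongly on the shape of the changes: uniform 40 points, normal 21, contaminated normal 16, logistic 15, t with 5 df 13, t with 3 df 9, Laplace 3.

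**5. All 120 pooled.** At about 80% Wilcoxon power the normal-case loss is 15 points (65% v 80%). For Laplace changes Friedman alone is ahead by 4 points (84% v 80%), though the gated sequence still loses (76%).

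**6. How often the two tests disagree.** For normal changes of 0.47 SD at n = 40, exactly one test is significant in 61% + 81% − 2 × 60% = 22% of trials.

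**7. Wilcoxon's own assumption.** When the differences themselves were lognormal and centred at median zero, Wilcoxon rejected in 10% of trials at n = 40 and 22% at n = 120.

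**The case against.** The strongest reply is that the remedy is already in the plan. Wilcoxon is named in the next sentence, and with one pair the Bonferroni factor is 1, so a literal reading gives an uncorrected Wilcoxon test of post versus pre. This stands in part: power is lost only if Friedman decides or gates. A reader might infer a gate because the Tukey sentence has one, but the Mann-Whitney and Wilcoxon sentences have none. Without a gate, however, the plan is left with two tests and no deciding rule.

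A reader might also infer a fixed loss of 14 to 20 points, or that Friedman is the least efficient test available. Neither is supported. The documents give no distribution or effect size for the changes, the loss is small for Laplace changes, and the order reverses in the pooled Laplace case. It is also fair to say that Friedman is reserved for variables judged non-normal, so normal changes should not set the headline. Against that, the normality check is on the variables and not explicitly on the differences, and the skewed-score rows show losses of 16 to 19 points.

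The objection that Wilcoxon needs symmetry stands as a caveat. If pre and post are exchangeable within person under the null, the differences are symmetric, and Wilcoxon held 4.7 to 5.2% in the scenarios simulated that way. Those scenarios say nothing about differences that are themselves skewed around a zero median.

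Finally, a reader might suppose that the randomised comparison or the sample size is weakened. It is not: the non-normal group comparison uses Kruskal-Wallis and Mann-Whitney, and 120 comes from a between-group calculation.

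**Conclusion.** The point holds in a limited form. It is certain from the documents that two time points make Friedman the sign test, and that the plan names two tests for one contrast without saying which decides.

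The cost is conditional on Friedman deciding or gating. Under the working assumptions (40 per arm, within-arm analysis, moderate effects) it is about 15 to 20 points of power for normal changes or moderately skewed scores and about 3 to 4 points for Laplace changes when Friedman decides. A gate adds slightly to these losses in most cases, rising to 8 points for Laplace changes, and also makes the procedure conservative. The documents do not support a claim that real changes will be reported as absent. The effect is confined to within-person tests of change over time.

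**What to change.** In both the Statistical Analysis Plan and the Statistical Methodology row of the summary, replace Friedman and its Wilcoxon follow-up with one Wilcoxon signed-rank test of post versus pre, named as the deciding test of change for non-normal variables. State in the same sentence whether it is run within arm or pooled, and that it is two-sided if that is intended.

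Removing the Bonferroni step for time pairs and the Greenhouse-Geisser sentence is tidying only: with one pair and two levels neither can alter a result.

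The cost is wording. The data are the same and the test is already in the plan. The price is reliance on roughly symmetric differences, so the differences should be inspected and a markedly skewed set reported with that caution.

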YEDITEPE UNIVERSITY

STUDY PROTOCOL AND STATISTICAL ANALYSIS PLAN

The Acute Influence of Proprioceptive Neuromuscular
Facilitation on Cervical Proprioception and Range of Motion.

Date: 25/02/2019

NCT Number:
NCT04045106

Prepared by:

[name]

ISTANBUL/TURKEY

Study Summery

Title	The acute influence of Proprioceptive neuromuscular facilitation on cervical proprioception and range of motion.
Methodology	Randomized, controlled trial, double blinded study
Study Duration	The estimated time for participants recruitment, screening and protocol implantation is 20 days
Study Location	University Labs
Subjects	120 healthy subjects randomized to 3 arms: 2 treatment and 1 control Inclusion criteria: To determine if a participant is healthy a score of 5 or less on the neck disability index will be used, no history of cervical trauma, rheumatic diseases, whiplash syndrome, no history of surgeries to the neck, face and shoulders, no history of cancer, no history of systemic diseases, age of 18 or above and able to understand and follow instructions.
Assessment	Cervical Proprioception using cervical range of motion (CROM) instrument, Active Range of motion (AROM) using CROM instrument, Muscle strength using a myometer device.
Intervention	PNF Pattern: Dynamic of reversals technique, PNF stretching: contract-relax-antagonist contract (CRAC) technique, control group: ineffective passive ROM.

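### The protocol and SAP name no primary outcome, analysis unit or testing order, so the 5% error level and 80% power belong to no identifiable result

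*Combined protocol and SAP*

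**What the plan says.** The title covers two domains: "The Acute Influence of Proprioceptive Neuromuscular Facilitation on Cervical Proprioception and Range of Motion". The Assessment row of the summary table lists three without ranking them: "Cervical Proprioception using cervical range of motion (CROM) instrument, Active Range of motion (AROM) using CROM instrument, Muscle strength using a myometer device". The Background information section argues for the study from one of them ("Due to the importance of cervical proprioception and the lack of studies in literature"), but the purpose that follows covers all three: "investigate the acute influence of proprioceptive neuromuscular facilitation on cervical proprioception, range of motion and strength".

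Each domain has six measures. For proprioception: "Cervical proprioception was done for flexion, extension, right side bending, left side bending, right and left rotation". For range of motion: "AROM was taken for all movement directions", and the CROM description counts six directions. Strength is taken for six muscle groups, one per direction. No composite or domain score is defined.

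The Sample Size section gives power 0.80, alpha 0.05 and "effect size of 0.25 with number of measurements being 2, which total to 120 participants". It does not say which outcome the effect size describes.

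The Statistical Analysis Plan refers only to variables and measurements in general. It plans an overall group test followed by Tukey, or Kruskal-Wallis followed by Bonferroni-corrected pairwise tests, plus separate tests of change over time. It closes with one level: "A 5% type-I error level was used to infer a statistical significance".

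**The concern.** A 5% error rate and 80% power are properties of a specified test on a specified variable. Here neither has a target. A significant result in any domain, or in any single direction, could afterwards be presented as the trial's finding, and no sentence in the plan would contradict it. That does not depend on any simulation.

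The planned multiplicity steps do not help, because they cover the three group contrasts (or the time contrasts) inside one variable. Nothing controls error across directions or domains, so the chance of a false PNF finding rises with the number of measures tested. How far it rises depends on the analysis unit and on correlations that the documents do not give.

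**Working it through.** **1. Reproduce the sample size.** Inputs from the Sample Size section: repeated-measures ANOVA, between factors, f = 0.25, m = 2 measurements, alpha 0.05, power 0.80; three arms. The correlation rho between measurements is not stated.

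Formula: lambda = f² × N × m / (1 + (m − 1) × rho), with df 2 and N − 3.

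- rho = 0.5, N = 120: lambda = 0.0625 × 120 × 2 / 1.5 = 10.0, power 0.805.
- rho = 0.5, N = 117: lambda = 9.75, power 0.794.
- rho = 0.3 would need 105 participants, and rho = 0.7 would need 135.

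So 120 reproduces at rho = 0.5. The arithmetic is sound, but it concerns an unidentified variable.

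**2. Count the measures.** 3 domains × 6 directions = 18.

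**3. Illustrate the error rate.** Assumptions: equal allocation (40 per arm; no ratio is stated), normal data, no true effect anywhere, and all correlations assumed. Each variable gets a one-way ANOVA at 5% (critical F 3.074) and, if significant, Tukey (critical q 3.357, df 117). The event counted is at least one significant difference between a PNF arm and control. The Kruskal-Wallis route and the time tests are not counted.

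One outcome gives 3.25%. It is below 5% because PNF-versus-PNF differences are not counted and both the overall test and Tukey must be significant. For several outcomes with a common correlation (30,000 replicates for three scores, 12,000 for 18 directions):

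| Correlation | 0 | 0.3 | 0.5 | 0.7 | 0.8 | 0.9 |
|---|---|---|---|---|---|---|
| Three domain scores | 9.3% | 9.2% | 8.5% | 7.4% | 6.8% | 5.8% |
| 18 directions | 44.4% | 39.0% | 30.4% | 21.9% | 16.9% | 11.4% |

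Closed-form check under independence: 1 − (1 − 0.0325)³ = 9.4%, and 1 − (1 − 0.0325)¹⁸ = 44.8%. A longer run of 200,000 replicates gives 44.7% for 18 independent directions and 11.2% at 0.9.

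If correlation is higher within a domain than between domains, the 18-direction rate is 41.5% at 0.3/0.1 and 19.0% at 0.9/0.5. Six proprioception directions alone give 18% at correlation 0 and 8% at 0.9. All rates fall towards 3.25% as correlations approach 1.

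**4. Power of a single primary score with 120 participants.** Baseline-adjusted group test: lambda = f² × N / (1 − r²), df 2 and 116, with r the assumed pre-post correlation. If f = 0.25 refers to the score itself, r = 0.3, 0.5 and 0.7 give lambda = 8.24, 10.0 and 14.7, and power 72%, 80% and 93%.

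If instead f = 0.25 holds per direction, take the same shift d in both PNF arms. Then f = d × √2 / 3, so d = 0.530 SD. A mean of six directions with inter-direction correlation c has SD √((1 + 5c)/6). With r = 0.5:

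| Inter-direction correlation | 0.3 | 0.5 | 0.7 | 0.8 |
|---|---|---|---|---|
| Effect in all six directions: power | 99% | 96% | 91% | 87% |
| No effect on side bending in either PNF arm: f = (4/6) × 0.25 / SD | 0.258 | 0.218 | 0.192 | 0.183 |
| The same case: power | 83% | 68% | 57% | 52% |

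**The case against.** *Proprioception is primary in all but name.* It comes first in the title and purpose, its importance is the stated rationale, and the title omits strength. That is a fair reading of emphasis, but order is not designation, and the title gives range of motion a place as well. Even if proprioception were accepted as primary, its six directions have no summary score.

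*A primary outcome may be registered elsewhere.* The document carries a registration number, and that record has not been seen. The point is therefore limited to this protocol and SAP. They should be able to stand alone on what their own error level refers to.

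*The percentages do not measure this trial's error rate.* This stands. A reader might infer that the trial has a 45% false-positive rate, or that the SAP plans 18 separate tests. The documents support neither. The 45% needs 18 independent measures, which is not to be expected for six directions on one neck, and the SAP never says whether directions are tested singly, averaged or otherwise combined. Nor should a reader infer that 120 is a miscalculation, since it reproduces.

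*This is a one-session study in healthy volunteers with an open purpose.* This has some force: an exploratory label is a legitimate alternative, and the fix allows it. But a randomised trial that states 5% error and 80% power needs a result for those figures to describe.

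*A composite with gating goes further than the defect requires, and can lose power.* This also stands in part. Only the naming of a unit and a primary outcome is necessary; the rest is one workable form. The power illustration holds the score's pre-post correlation at 0.5, which averaging may raise. If correlations across time and direction are also 0.3, it becomes (0.5 + 5 × 0.3)/(1 + 5 × 0.3) = 0.8, and the 83% becomes 99%.

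**Conclusion.** The concern holds as a gap in this protocol and SAP. No primary outcome, analysis unit or testing order is named, f = 0.25 belongs to no variable, and no adjustment crosses outcomes. The stated 5% and 80% therefore describe no identifiable result. This conclusion rests on the text alone, and the plan should be corrected before any confirmatory claim is made.

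The size is illustrative. Over one common correlation range of 0 to 0.9, the chance of at least one false PNF-versus-control difference goes from 3.25% for a single outcome to about 6-9% for three domain scores, or about 11-45% if each direction is tested. These figures assume 40 per arm, normal data, a global null, the ANOVA-plus-Tukey route only, and correlations that the documents do not supply. No lower bound above 3.25% is claimed.

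**What to change.** **Required.** Before unblinded data are examined, state the analysis unit and name one primary outcome with a fixed test, to which the 5% level and the sample-size sentence both refer. The choice is the sponsor's.

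**One workable form.**
- Primary: mean absolute deviation from the 30-degree target over the 3 trials and 6 directions after the intervention, compared between groups at 5% with adjustment for its baseline value, followed by Tukey contrasts.
- Secondary: one AROM score and one strength score. Either test them with Holm across the two, only if the primary group test is significant, or report them with confidence intervals. If they are tested, state the level for their pairwise contrasts too.
- Exploratory: single directions, with confidence intervals.

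**Alternative.** If data have already been examined, or the sponsor prefers not to name a primary, label all results exploratory. The document mixes past and future tense, so its own text does not settle whether data had been seen.

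**Cost.** SAP wording and a restated sample-size sentence, with no new data. Single-direction results are no longer confirmatory. Under gating, AROM (half of the title) and strength are not confirmatory either if proprioception is not significant. A six-direction score gains power when the effect is general and can lose it when the effect is confined to some directions. The sponsor should weigh this when choosing the score.
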